4. AIMS AND ENDPOINTS

Aim 1. Examine the effects of CAA on alcohol outcomes. Our primary hypothesis is that, relative to AO control, the CAA intervention will (a) increase positive moderate drinking attitudes, (b) decrease positive heavy drinking attitudes, (c) increase attitude-behavior dissonance, and (d) decrease drinks per drinking day, binge frequency, peak BAC, and alcohol consequences, and increase the use of PBS.

Aim 2. Compare the effects of CAA vs. PNF. A secondary hypothesis is that CAA will be no less efficacious than (i.e., not inferior to) PNF in reducing alcohol outcomes as measured by alcohol consumption and alcohol related consequences.

Aim 3. Test specific theory-based mediational pathways. Aim 3a. We predict that the effects of the CAA intervention on alcohol consumption and consequences will be mediated by increases in (a) positive attitudes towards moderate drinking and (b) dissonance (but not perceived norms). Aim 3b. We predict that the effects of the PNF intervention on alcohol

consumption and consequences will be mediated by decreases in (a) perceived descriptive norms and (b) dissonance (but not attitude change).

Aim 4. Test intervention-specific moderators of outcome. Aim 4a. We predict that the effect of the CAA intervention will be enhanced by stronger drinker identity, greater need for consistency, and will not differ by study site. Aim 4b. We predict that response to the PNF condition will be enhanced by weaker drinker identity, greater need for consistency, and will be stronger within a lighter drinking community (the Houston site).

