5. STUDY DESIGN

We will use a multi-site randomized controlled trial (RCT) to evaluate the effects of counter attitudinal advocacy (CAA) relative to assessment only (AO) control on drinking and related problems among college students, and the relative effects of CAA vs. PNF on relevant drinking outcomes. Eligible students will be randomly assigned to one of 3 conditions (personalized CAA or PNF or AO control). Hypothesized mechanisms of change (alcohol-related attitudes and dissonance, perceived drinking norms) will be evaluated immediately after the intervention (posttest) and drinking outcomes (drinks per week, heavy drinking frequency, peak BAC, alcohol-related problems, PBS) will be evaluated at 1-, 3-, and 6-months post-intervention. All procedures are conducted for the purpose of research only.

We propose to conduct this study at two sites (both Carnegie Tier 1 Research universities) that have distinctly different campus and student profiles in order to explicitly test hypotheses about the differential efficacy of CAA vs PNF in different campus contexts. Brown University is a private residential 4-year college with approximately 6200 undergraduates (51% female and 43% minority) and characteristics associated with higher risk of alcohol misuse (e.g., Northeast region, Greek system, athletic tradition). All first- and second-year students and most third-year students live together in on-campus dorms. Students at Brown report high rates of drinking: 81% of Brown students drank in the past 3 months, and 51% report binge drinking in the last two weeks. In contrast, the University of Houston (UH) is a large public research university serving more than 34,716 undergraduate students (51% female and 74% minority). Roughly 80% of UH students live off campus. Located in America's fourth-largest city, UH was designated as the most ethnically diverse metropolitan research university in the United States by Forbes in 2010. UH students report a below average drinker profile, with 45% of the students reporting current drinking and 23% report binge drinking in the last month. Overall, the base rates for any drinking and binge drinking are lower at UH than at Brown. These two sites allow us to test the comparative efficacy of CAA vs PNF in contexts with both high and low base rates of heavy drinking. If site does not moderate efficacy, then the replication of the effects of CAA across sites will provide evidence of generalizability of observed effects.

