10. STATISTICAL CONSIDERATIONS

10.1. Sample Size. Power analyses focus on estimating a sample size large enough to detect “true” effects, thereby avoiding Type II errors. Sample size estimates were obtained for intervention contrasts. Necessary sample sizes were assessed via sample size and power equations for multi-level models using the Optimal Design software program. Based on previous findings using CAA and PNF approaches, we anticipate intervention effects relative to the neutral control condition to be in the small to medium range but at least comparable to effects which have been reported for personalized normative feedback, which are typically in the .28 range (e.g., Dotson et al., 2015). Based on the proposed sample size of 600, given four assessment points, we anticipate the ability to detect effects of intervention contrasts and moderation effects across the small to medium range. Considering maximum anticipated attrition rates of 15% (N=510) we will have .70, .80, and .90 power to detect effects sizes of $\delta = .24, .27, \text{ and } .32$, respectively.

10.2. Analysis Plan. Aims will be evaluated using generalized linear mixed models, an extension of general linear models allowing for multi-level data with non-normal distributions (e.g. Atkins, Baldwin, Zheng, Gallop, & [name], 2013; Hedeker & Gibbons, 2006). With respect to evaluating main effects of experimental conditions on drinking, each participant will provide up to four assessments (baseline, 1-month, 3-month, and 6-month follow-up data). Hypotheses will be tested using specific contrast vectors, using a general linear hypothesis framework (Fox, 2008).

Hypotheses associated with Aim 1 will be evaluated examining outcomes as a function of two dummy coded variables representing CAA and PNF with control as the reference group. Time X CAA outcomes will provide direct tests of differences in change between CAA and control groups. We will utilize a Bonferroni correction with Šídák adjustment for correlated outcomes to reduce alpha inflation associated with multiple outcomes (i.e., moderation attitudes, heavy drinking attitudes, dissonance, drinks per drinking day, binge frequency, peak BAC, alcohol consequences, and PBS use).

For these analyses, each participant will provide up to 4 repeated measures (i.e., baseline, 1-month, 3- months, 6-months), yielding up to 2400 Level 1 cases (repeated-measures) across 600 Level 2

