cases). Assuming outcomes follow a negative binomial distribution with a natural log link, the following model will be the basis for evaluating intervention effects as specified in Aim 1 hypotheses:

$$\text{Level 1: } \log(E[\text{DV}]_{ti}) = \pi_{0i} + \pi_{1i}(\text{Time})_{ti} + \varepsilon_{ti} \quad \varepsilon_{ti} \sim N(0, I\sigma^2_\varepsilon)$$

$$\begin{aligned} \text{Level 2: } \pi_{0i} &= \beta_{00} + \beta_{01}(\text{site})_i + \beta_{02}(\text{CAA})_i + \beta_{03}(\text{PNF})_i + \beta_{10} + r_{00i} \\ \pi_{1i} &= \beta_{10} + \beta_{11}(\text{site})_i + \beta_{12}(\text{CAA})_i + \beta_{13}(\text{PNF})_i + r_{10i} \end{aligned}$$

where t indexes repeated-measures and i indexes participants. Campus represents the differences between Brown and UH, CAA represents the difference between CAA and the Control group, and PNF represents the difference between PNF and the control group. DV_{ti} represents the outcome vector for each individual at each assessment point. Time_{ti} measures weeks since baseline. Hypotheses associated with Aim 2 will test the relative efficacy of CAA vs. PNF using a non-inferiority design. Following the procedures outlined by Schumi & Wittes (2011), we have consulted a recent metaanalysis to obtain an effect size estimate of PNF efficacy (vs. Control) on drinking quantity ($d = .289$, 95% CI [0.117, 0.451]) and consequences ($d = .157$, 95% CI[0.037, 0.278]) (Dotson, Dunn, & Bowers, 2015). Next, we use the lower bound of each confidence interval as the basis for deriving our margin with respect to declaring non-inferiority. Thus $M1 = 0.117$ for quantity and $M1 = .037$ for consequences; these represent the most conservative estimate of the PNF effect. Then we select a smaller margin (M2) that represents the largest acceptable loss of effect when CAA is compared to PNF. Using a conservative estimate of M2 (50% of M1; USFDA, 2016), we establish non-inferiority if we retain at least half of the effect of PNF. Thus, if the lower bound confidence interval for the effect of CAA vs PNF is larger than half the lower bound estimate of the effects on drinking quantity (.117/2 = .0585) and consequences (.037/2 = .0185), we will be able to declare CAA is non-inferior to PNF.

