Hypotheses associated with Aim 3 will evaluate mediators of intervention effects. We will follow procedures described by MacKinnon and colleagues (e.g., MacKinnon, Fairchild, & Fritz, 2007) to assess mediation. Mediation will test indirect effects using the AB products method with bootstrapped standard errors where A will represent effects of intervention contrasts by time interactions on mediators. B will represent the associations of mediators on subsequent drinking outcomes. Both A and B paths will control for baseline outcomes. Hypotheses associated with Aim 4 will follow a similar approach but will add prospective moderators and products of prospective moderators and contrasts

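### As written, the Aim 1(c) dissonance test omits the posttest, so a rise that resolves before 1 month has an expected Time × CAA slope of zero

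*Combined protocol and SAP*

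**What the plan says.** Section 4 lists the components of the primary hypothesis for CAA relative to AO; one is "c) increase attitude-behavior dissonance".

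Section 5 separates two schedules. For mechanisms: "Hypothesized mechanisms of change (alcohol-related attitudes and dissonance, perceived drinking norms) will be evaluated immediately after the intervention (posttest"). Drinking outcomes are placed at 1, 3 and 6 months. Section 9.1.4 describes the Dissonance Thermometer as a rating of how participants feel straight after the CAA activity.

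Section 10.2 names the eight outcomes that share the multiplicity adjustment: "moderation attitudes, heavy drinking attitudes, dissonance, drinks per drinking day, binge frequency, peak BAC, alcohol consequences, and PBS use". The test is given as "Time X CAA outcomes will provide direct tests of differences in change between CAA and control groups". The next paragraph says that for these analyses "each participant will provide up to 4 repeated measures (i.e., baseline, 1-month, 3- months, 6-months"), giving up to 2400 records from 600 participants. The model that follows is presented as the basis for the Aim 1 hypotheses. It has a single linear Time term, where Time "measures weeks since baseline".

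Section 10 nowhere mentions the posttest. For mediation (Aim 3) it says "A will represent effects of intervention contrasts by time interactions on mediators", again without naming it. A posttest survey does exist: section 11.2 refers to linking it to the baseline and follow-up surveys.

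**The concern.** The protocol measures this hypothesis at one time and tests it with data from other times. Dissonance is evaluated minutes after the activity, while the stated test uses a pre-activity value and three values at least a month later. A slope fitted to those four visits carries no information about a difference present only at posttest.

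At stake is one component of the primary hypothesis. CAA could produce the immediate response that sections 5 and 9.1.4 are set up to capture, and the prespecified test could still return a null result or one of the wrong sign. The two attitude outcomes (Aim 1(a) and (b)) need the same clarification, because section 5 places them at posttest too.

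**Working it through.** **Is the posttest in the Aim 1 data?** The plan's count reproduces: 600 × 4 = 2400. With the posttest it would be 600 × 5 = 3000.

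**What does the slope see?** Let D be the CAA minus AO excess in dissonance, zero before the activity. Visits are at 0, 1, 3 and 6 months (section 10.2). The mean is 2.5, the deviations are −2.5, −1.5, +0.5 and +3.5, and Sxx = 6.25 + 2.25 + 0.25 + 12.25 = 21. The difference in slope, expressed as change over 6 months, is the sum of (6 × deviation / 21) × excess. The weights are −15/21, −9/21, +3/21 and +21/21, that is −0.714, −0.429, +0.143 and +1.000. Weeks give the same result.

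| Excess at 0, 1, 3, 6 months | Slope × 6 months |
|---|---|
| 0, 0, 0, 0 (resolved before 1 month) | 0 |
| 0, D, 0, 0 | −0.43 × D |
| 0, D, D/2, 0 | −0.429D + 0.071D = −0.36 × D |
| 0, D, D/2, D/2 | −0.357D + 0.500D = +0.14 × D |
| 0, D, D, D (persistent) | +0.71 × D |
| 0, 0, 0, D | +1.00 × D |

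If the excess halves by month 3, the slope is positive only if more than 0.429 − 0.071 = 0.357 of D remains at month 6.

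These are identity-link values. With the plan's log link (assumed: control mean 2, dispersion 0.5, D a log ratio of 0.3), the six rows become 0, −0.47, −0.39, +0.10, +0.67 and +1.02. The zero in the first row depends on neither link nor correlation.

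**Would adding the posttest as a row at week 0 help?** No. Visits 0, 0, 1, 3 and 6 have mean 2 and Sxx = 4 + 4 + 1 + 1 + 16 = 26. The posttest weight is 6 × (−2)/26 = −0.462, so a posttest-only rise gives −0.46 × D.

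**What would a separate posttest contrast achieve?** Assumed inputs: a posttest-only rise of 0.28 SD (the plan's figure for normative feedback effects, not a dissonance estimate) and correlation r with the pre-activity score of 0.3 to 0.7. From section 6.1, 200 per arm. SE = √[(2/200)(1 − r²)], and power ≈ Φ(0.28/SE − z). The plan states no alpha. I take two-sided 0.05 (z = 1.960) and full Šídák for eight outcomes, 1 − 0.95^(1/8) = 0.0064 (z = 2.727). The plan's adjustment for correlated outcomes would fall between them.

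| r | SE | 0.28/SE | Power at 0.05 | Power at 0.0064 |
|---|---|---|---|---|
| 0.3 | 0.0954 | 2.935 | 0.84 | 0.58 |
| 0.5 | 0.0866 | 3.233 | 0.90 | 0.69 |
| 0.7 | 0.0714 | 3.921 | 0.98 | 0.88 |

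With 170 per arm (15% attrition) the ranges are 0.77 to 0.95 and 0.49 to 0.81. In the same scenario the stated slope test rejects at its alpha; a simulation of 5000 trials (r = 0.5, 170 per arm) gave 4.9%.

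**The case against.** **Section 10.2 may have been written with drinking in mind.** It first introduces the four waves this way: "With respect to evaluating main effects of experimental conditions on drinking, each participant will provide up to four assessments". The model assumes a negative binomial count, which does not suit a rating scale, and section 5 keeps the schedules apart. Loose drafting is a fair explanation. But the later sentence about these analyses directly follows a list that includes dissonance, and the model is tied to the Aim 1 hypotheses as a whole. On the charitable reading dissonance has no stated analysis, and the same sentences are needed.

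**The plan allows specific contrast vectors.** It does, but no contrast can recover a time point missing from the fitted data.

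**The harm depends on decay.** This stands. Section 8.1 says dissonance can be resolved by behavior change, without saying when. A reader might infer that the stated test cannot detect dissonance at all. The documents do not support that, because a sustained or late excess gives a positive slope.

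**The power comparison rests on borrowed inputs.** This stands too. It shows that a posttest contrast is workable, not what this trial would lose.

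**A reader might infer that the Thermometer is dropped at follow-up, so that the model cannot be fitted.** The debrief script in Appendix C does call the follow-up surveys much shorter. Section 9.2, however, says the follow-up measures match baseline, and a shorter survey need not lack this scale.

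**Conclusion.** The concern holds for the plan as written: the stated Aim 1(c) test leaves out the time point at which the protocol evaluates dissonance, and nothing else in section 10 restores it. The expected slope is zero for a rise that resolves before 1 month. It can be negative for one that fades during follow-up (−0.36 to −0.43 × D in the patterns shown) and is positive only when enough excess is sustained or appears late (+0.14 to +1.00 × D). The weights assume complete data. Which pattern would occur is unknown, so this is a mismatch between test and hypothesis, not a forecast that Aim 1(c) will fail.

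The scope is limited. One of eight outcomes is clearly affected, and the time point for the two attitude outcomes needs stating. The tests on drinking, consequences and protective strategies are untouched. The plan should be corrected, but this does not threaten the trial.

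**What to change.** In section 10.2:

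- Make the primary test of Aim 1(c) the CAA vs AO difference in Thermometer score at posttest, adjusted for the pre-activity score where collected, with a distribution suited to the scale. Specify it as a separate contrast, not as an extra row in the linear-time model.
- Keep it as one of the eight multiplicity-adjusted outcomes, and label any dissonance test at 1, 3 and 6 months as secondary.
- State whether the posttest is also the primary time point for the two attitude outcomes.

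The cost is a few sentences, with the outcome count unchanged. No new data are needed provided AO completed the Thermometer in its closing questions. Section 5, the posttest survey in section 11.2 and the control-arm script in Appendix C imply this, but none states it and the survey screens are not shown. The sponsor should confirm it first, because AO participants already enrolled could not supply a posttest score afterwards.

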9.1.2. Primary and secondary outcomes

Alcohol consumption will be assessed with the Quantity-Frequency-Peak Alcohol Use Index (QFP; Baer, 1993; Marlatt, Baer, & Larimer, 1995), and the Daily Drinking Questionnaire (DDQ; Collins, Parks, & Marlatt, 1985; Kivlahan, Marlatt, Fromme, Coppel, & Williams, 1990). The Quantity-Frequency-Peak Alcohol Use Index is a five-item questionnaire that includes two items characterizing the occasion where respondents drank the most during the previous month (from which we calculate peak BAC), two items addressing typical weekend drinking in the previous month, and one item addressing typical number of drinking days per week in the past month. Typical weekly drinking and typical drinks per occasion will be assessed with the DDQ. Participants fill in the average number of standard drinks they consumed and the time period of consumption for each day of a typical week in the past month. The primary source for assessing drinking outcomes will be the DDQ, and QFP, which we have used in several previous RCTs in this population.

Alcohol-related negative consequences will be assessed with the 48-item Young Adult Alcohol Consequences Questionnaire (YAACQ; (Read, Kahler, Strong, & Colder, 2006). The YAACQ is a self-administered checklist of problems related to drinking that is tailored to college drinkers; responses are dichotomous (yes/no) and refer to past month. The YAACQ is reliable and free of gender bias.

Protective behavioral strategies will be measured with the 15-item Protective Behavioral Strategies Scale (Martens, Pedersen, LaBrie, Ferrier & Cimini, 2007) The PBSS assesses contingent frequency of using each strategy when drinking (1=never, 6=always) and is reliable and valid for use with college drinkers. This will be supplemented with the 4-item “Alternatives to drinking” factor (e.g., “Found other ways besides drinking to reduce stress”) from the Protective Behavioral Strategies Questionnaire (Sugarman & Carey, 2007).

Drinking intentions will be assessed using a modified version the daily drinking questionnaire (DDQ; Collins, Parks, & Marlatt, 1985; Kivlahan, Marlatt, Fromme, Coppel, & Williams, 1990: Modified DDQ Intentions; Young, Rodriguez, & [name], 2013). Participants fill in the average number of standard drinks they intend to consume and the time period of intended consumption for each day of a typical week in the next month.

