9.1.4. Hypothesized mediators

Attitudes toward moderate consumption and attitudes toward heavy consumption will be assessed with measures modified from previous research (Hagger et al., 2012; Norman, 2011). For moderate consumption, the stem will read, "Keeping my alcohol drinking within what is considered moderate drinking for adults (i.e. at 4 or fewer drinks for men or at 3 or fewer drinks for women) on each individual occasion over the next month would be..." For heavy consumption, the stem will read, "Having five or more drinks (for males)/four or more drinks (for females) in a sitting over the next month would be..." For both measures, there are five semantic differential scales that range from 1 to 5: unenjoyable-enjoyable, bad-good, harmful-beneficial, foolish-wise, and unpleasant-pleasant. To test AIM 3, changes in attitudes toward heavy drinking and attitudes toward moderate drinking are anticipated to serve as a mediator of the CAA (but not PNF) intervention effects.

Cognitive dissonance will be assessed using the Dissonance Thermometer (Devine, Tauer, Barron, Elliot, & Vance, 1999; Elliot & Devine, 1994; Simmons & Brandon, 2007; Simmons et al., 2004; Simmons, et al., 2013). Items include asking participants how uncomfortable, angry at themselves, shameful, uneasy, friendly (reverse scored), disgusted with themselves, embarrassed, bothered, optimistic (reverse scored), annoyed at themselves, disappointed at themselves, happy (reverse scored), energetic (reverse scored), and good (reverse scored) they feel immediately following the CAA activity. The 3-item affective discomfort factor has been found to be susceptible to cognitive dissonance inductions resembling our CAA procedure, with other target behaviors (Devine et al., 1999; Simmons et al., 2013). In Aim 3 we will test dissonance as a mediator of both CAA and PNF interventions.

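### Section 10.2 bases all eight Aim 1 tests on a negative binomial model, but five outcomes are not counts; for underdispersed scores the Time x CAA test is too conservative

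*Combined protocol and SAP*

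**What the plan says.** Section 10.2 adopts generalized linear mixed models, described as "an extension of general linear models allowing for multi-level data with non-normal distributions". It lists the Aim 1 outcomes for multiplicity control: "i.e., moderation attitudes, heavy drinking attitudes, dissonance, drinks per drinking day, binge frequency, peak BAC, alcohol consequences, and PBS use". The test is the interaction with time: "Time X CAA outcomes will provide direct tests of differences in change between CAA and control groups". The model itself follows: "Assuming outcomes follow a negative binomial distribution with a natural log link, the following model will be the basis for evaluating intervention effects". Its level-1 equation also carries an additive normal error.

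Section 10.2 assigns no other family or link to any Aim 1 outcome and gives no rule for choosing one. It does not say whether Aim 1 standard errors are model-based or robust.

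The measures are described in section 9.1:

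- **Attitudes** (9.1.4): "there are five semantic differential scales that range from 1 to 5".
- **Dissonance** (9.1.4): ratings of feelings, some reverse scored. "The 3-item affective discomfort factor has been found to be susceptible to cognitive dissonance inductions resembling our CAA procedure".
- **PBS use** (9.1.2): "The PBSS assesses contingent frequency of using each strategy when drinking (1=never, 6=always"), plus four supplementary items.
- **Peak BAC** (9.1.2): calculated from two items about the heaviest occasion.
- **Consequences** (9.1.2): 48 yes/no items, so a count.
- **Drinks** (9.1.2): the DDQ asks for averages by day of a typical week, so drinks per drinking day need not be a whole number.

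**The concern.** A negative binomial describes whole numbers from zero upwards, with variance at least equal to the mean. Bounded rating scores that cannot be zero do not behave like that, and neither does a calculated concentration. The random intercept absorbs differences between people. What remains within a person may vary less than the mean, and the model cannot represent that: the dispersion term goes to zero and the residual variance stays at the mean. Model-based standard errors are then too large.

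Attitude change and dissonance are the mechanism that CAA is meant to work through, and section 4 places them in the primary hypothesis. A missed effect there would misinform the trial's main question. A whole-number sum score would be fitted without any software warning.

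**Working it through.** **Inputs.** From the documents: three arms, N = 510 after 15% attrition, so 170 per arm; baseline and 1, 3 and 6 months (taken as weeks 0, 4, 13, 26); attitude items 1 to 5, so a five-item sum runs from 5 to 25. Assumed, because the documents give no values: attitude sum mean 15, SD 4.5; within-person correlation r = .5 or .7; d = 0.28 at 6 months (section 10.1 puts PNF effects near .28); no dropout beyond the 170. The plan states no figure of its own on this point. Paired results below are for r = .5 / .7.

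**Step 1: standard error factor.** With no true variation in slopes, F = sqrt(mean / within-person variance), and not less than 1. Within-person variance is 4.5² × (1 − r) = 10.125 / 6.075.

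- F = sqrt(15/10.125) = 1.22; sqrt(15/6.075) = 1.57.
- Simulation with scores rounded and held to 5–25 gives about 1.3 / 1.6.

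**Step 2: power of a linear model.** The four times have sum of squares about their mean of 398.75. The slope difference is 0.28/26 = 0.01077 SD per week.

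- r = .5: SE = sqrt(2 × 0.5/398.75/170) = 0.00384; ratio 2.804; power Φ(2.804 − 1.96) = 80%.
- r = .7: SE = sqrt(2 × 0.3/398.75/170) = 0.00298; ratio 3.620; power Φ(3.620 − 1.96) = 95%.

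**Step 3: power of the negative binomial.** The estimate varies as before, but its stated standard error is F times too large, so power ≈ Φ(ratio − F × 1.96). With the Step 1 closed-form factors this is Φ(2.804 − 2.391) = 66% and Φ(3.620 − 3.077) = 71%. Simulation gives 59% to 61% and 63% to 68%, or about 59% / 65%.

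**Step 4: type I error.** At F = 1.3 / 1.6 the nominal 5% test rejects a true null with probability 2Φ(−F × 1.96) = 1.1% / 0.2%. The error is in the conservative direction only.

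**Step 5: true slope variation.** Let s be the SD of true 26-week change, in SD units. Per-person slope variance becomes (1 − r)/398.75 + (s/26)². The fitted slope variance can shrink to offset the inflated residual, so F falls. Power below uses the Step 2 and Step 3 formulas, except the first row's negative binomial entry, which is simulated.

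| s | F (r = .5 / .7) | Linear power | Negative binomial power |
|---|---|---|---|
| 0 | 1.3 / 1.6 | 80% / 95% | 59% / 65% |
| 0.5 | 1.1 / 1.35 | 69% / 84% | 62% / 62% |
| 0.75 | 1.0 / 1.1–1.2 | 58% / 70% | 58% / 56–63% |

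**Step 6: other assumed SDs.** With s = 0 and SD from 5.5 down to 3.5 (item-mean SD 1.1 to 0.7), F runs from 1.0 to 1.6 at r = .5 and from 1.3 to 2.0 at r = .7.

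**Step 7: other scorings, all assumed, s = 0.**

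- Summed PBS (mean 49.5, SD 12): within-person variance 72 / 43.2, F = 1.0 / 1.07.
- BAC in mg/dL (mean 120, SD 80): variance 3200 / 1920, F = 1.0.
- If the software fits non-integers: attitude item mean (3.0, SD 0.9) 2.7 / 3.5; PBS item mean (3.3, SD 0.8) 3.2 / 4.1; decimal BAC (.12, SD .08) 6.1 / 7.9.

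The same BAC data thus give F = 1.0 or above 6 depending only on the unit. Dissonance and drinks per drinking day were not simulated.

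**The case against.** **The framework is broad and the wording conditional.** Section 10.2 opens with generalized linear mixed models, and the model is introduced as an assumption and a basis. Another family would fit that framework. This is fair as to intent. However, the model follows directly on the eight-outcome list and is tied to the Aim 1 hypotheses without exception, so the plan as written applies it to all eight.

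**The loss depends on assumed values.** This stands. The 95% to 65% case needs high within-person correlation and no slope variation. The simulated scores were also generated as normal before rounding, which favours the linear comparator.

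**Attitudes and dissonance may be tested only at posttest.** Section 5 says: "Hypothesized mechanisms of change (alcohol-related attitudes and dissonance, perceived drinking norms) will be evaluated immediately after the intervention (posttest"). In an unadjusted posttest comparison the total variance 4.5² = 20.25 exceeds 15, so F = 1.0 and nothing is lost. Adjusted for baseline, variance is 20.25 × (1 − r²) = 15.19 / 10.33 and F = 1.0 / 1.2. With Time x CAA on baseline plus posttest, F returns to about 1.2 / 1.6. The last is closest to the stated test, but the timing is not settled.

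**Bootstrapping appears elsewhere.** Section 10.2 specifies bootstrapped standard errors for Aim 3, where attitudes and dissonance are mediators. That does not alter the Aim 1 test.

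**Stronger readings to avoid.** A reader might infer that every non-count outcome loses power; Step 7 shows otherwise. The factors of 6 and above for BAC might be read as expected; they need a decimal unit, model-based standard errors and software that accepts non-integers, none of which the documents state. Nor is it right that scoring rules are absent from the plan altogether: section 9.1 points to Appendix C, and the supplied appendix has only session scripts with figures missing.

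**Conclusion.** The concern holds. As written, section 10.2 applies a count distribution to five outcomes that are not counts. Where such a score is underdispersed and standard errors are model-based, the Time x CAA test is too conservative. For summed attitudes under the assumed values, the standard error is inflated by about 1.3 / 1.6 with no slope variation, 1.1 / 1.35 at a slope SD of 0.5 SD, and 1.0 / 1.1–1.2 at 0.75 SD. The loss is larger for item means or decimal BAC, but only if the software fits them. It is little or none for summed PBS, BAC in mg/dL or an unadjusted posttest comparison.

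A reader might infer a risk of spurious efficacy. The check shows the reverse: the risk is a missed effect. The direction follows from the distribution; the size rests on means, SDs, correlations and slope variation that the documents do not give. The change should be made, but the trial's validity does not hang on it.

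**What to change.** In section 10.2, name the family by outcome:

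- **Binge frequency and the YAACQ count:** keep the negative binomial with log link, and remove the additive normal level-1 error, since the distribution has its own dispersion term.
- **Both attitude scores, dissonance, PBS use and peak BAC:** linear mixed model (Gaussian, identity link) with person-clustered robust standard errors. These tests are then unchanged by the BAC unit or by using a sum or a mean of the same complete items.
- **Drinks per drinking day:** log-link model with person-clustered robust standard errors, which does not require whole numbers.

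The cost is SAP wording only, with no new data and no design change. The small downside is that results appear on two scales, rate ratios and mean differences.
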